4.1.2 Exclusion Criteria

- Use of non–protocol-specified anti-cancer therapies or other combination partners with carboplatin/etoposide during induction
- Symptomatic or actively progressing CNS metastases

Note: Asymptomatic patients with treated (i.e., local CNS-directed therapy) or untreated CNS lesions are eligible, provided that all of the following criteria are met:

- Measurable disease, per RECIST v1.1, must be present outside the CNS.
- The patient has no history of intracranial hemorrhage or spinal cord hemorrhage from CNS disease.
- Metastases are limited to the cerebellum or the supratentorial region (i.e., no metastases to the midbrain, pons, medulla, or spinal cord).
- The patient has no symptoms caused by CNS disease (i.e., no headache, nausea, vomiting, convulsion, paralysis, etc.).
- The patient has no ongoing requirement for anticonvulsants for CNS disease.
- The patient has no ongoing requirement for dexamethasone/corticosteroids for CNS disease (previously untreated patients must also not have any history of requiring or receiving dexamethasone/corticosteroids for CNS disease).
- For patients with previously treated CNS metastases, there is no evidence of interim CNS progression between the completion of CNS-directed therapy and enrollment.
- For previously untreated patients, there is no evidence of brain edema related to CNS disease (e.g., vasogenic edema).
- For previously untreated patients, a brain magnetic resonance imaging (MRI) scan with contrast is required at screening and is the preferred modality for all subsequent scheduled follow-up tumor assessments.

Note: Computed tomography (CT) scan with contrast may be acceptable for all subsequent scheduled follow-up tumor assessments if the following criteria are met.

 Both brain MRI and CT scan with contrast must be performed at screening to assess untreated CNS disease. The CT scan with contrast can be used to reliably evaluate lesions identified on the screening MRI with contrast.

If CT scan with contrast cannot be used to reliably evaluate lesions identified on the screening MRI with contrast, then MRI scan with contrast must be used at all subsequent scheduled follow-up tumor assessments.

The same modality must be used at every tumor assessment.

• Pregnant or breastfeeding, or intending to become pregnant during the study

Women of childbearing potential must have a negative serum pregnancy test result within 14 days prior to initiation of study drug.

- Spinal cord compression not definitively treated with surgery and/or radiation or previously diagnosed and treated spinal cord compression without evidence that disease has been clinically stable for ≥1 week prior to enrollment
- Leptomeningeal disease
- Uncontrolled pleural effusion, pericardial effusion, or ascites requiring recurrent drainage procedures (once a month or more frequently)

Patients with indwelling catheters (e.g., PleurX[®]) are allowed regardless of drainage frequency.

- Uncontrolled or symptomatic hypercalcemia (ionized calcium > 1.5 mmol/L, total serum calcium > 12 mg/dL, or corrected calcium > ULN)
- History of malignancy other than SCLC within 5 years prior to enrollment, with the exception of those with a negligible risk of metastasis or death (e.g., expected 5-year OS > 90%) treated with expected curative outcome (such as adequately treated carcinoma in situ of the cervix, basal or squamous cell cancer of the skin, localized prostate cancer treated surgically with curative intent, ductal carcinoma in situ treated surgically with curative intent)
- History of autoimmune disease, including but not limited to myasthenia gravis, myositis, autoimmune hepatitis, systemic lupus erythematosus, rheumatoid arthritis, inflammatory bowel disease, vascular thrombosis associated with antiphospholipid syndrome, Wegener's granulomatosis, Sjögren's syndrome, Guillain-Barré syndrome, multiple sclerosis, vasculitis, or glomerulonephritis

Patients with a history of autoimmune-mediated hypothyroidism on a stable dose of thyroid replacement hormone are eligible for this study.

Patients with controlled Type I diabetes mellitus on a stable dose of insulin regimen are eligible for this study.

Patients with eczema, psoriasis, lichen simplex chronicus, or vitiligo with dermatologic manifestations only (e.g., no psoriatic arthritis) are permitted provided that they meet the following conditions:

- Rash must cover less than 10% of body surface area.

- Disease is well-controlled at baseline and only requiring low potency topical steroids.
- No acute exacerbations of underlying condition within the last 12 months requiring treatment with either psoralen plus ultraviolet A radiation (PUVA), methotrexate, retinoids, biologic agents, oral calcineurin inhibitors, or high potency or oral topical steroids
- History of idiopathic pulmonary fibrosis, organizing pneumonia (e.g., bronchiolitis obliterans), drug-induced pneumonitis, idiopathic pneumonitis, or evidence of active pneumonitis on screening chest CT scan
 - History of radiation pneumonitis in the radiation field (fibrosis) is permitted.
- Positive test result for HIV

All patients must be tested for HIV; patients who test positive for HIV will be excluded.

• Active hepatitis B (chronic or acute; defined as having a positive hepatitis B surface antigen [HBsAg] test result at screening) or hepatitis C virus (HCV)

Patients with past hepatitis B virus (HBV) infection or resolved HBV infection (defined as the presence of hepatitis B core antibody [HBcAb] and absence of HBsAg) are eligible. HBV DNA should be obtained in these patients prior to enrollment and should be undetectable. These patients must be willing to undergo monthly DNA testing.

Patients positive for HCV antibody are eligible only if polymerase chain reaction (PCR) is negative for HCV RNA.

- Active tuberculosis
- Known infection with human T-cell leukemia virus 1
- Known active bacterial, viral, fungal, mycobacterial, parasitic, or other infection (excluding fungal infections of nail beds) at study enrollment, or any major episode of infection requiring treatment with IV antibiotics or hospitalization (relating to the completion of the course of antibiotics) within 4 weeks prior to Cycle 1, Day 1
- Significant cardiovascular disease, such as New York Heart Association cardiac disease (Class II or greater), myocardial infarction, or cerebrovascular accident within the previous 3 months, unstable arrhythmias, or unstable angina

Patients with known coronary disease, congestive heart failure not meeting the above criteria, or left ventricular ejection fraction <50% must be on a stable medical regimen that is optimized in the opinion of the treating physician, in consultation with a cardiologist if appropriate.

- Major surgical procedure within 28 days prior to enrollment or anticipation of need for major surgical procedure during the course of the study
- Prior allogenic bone marrow transplantation or solid organ transplant

- Any other diseases, metabolic dysfunction, physical examination finding, or clinical laboratory finding giving reasonable suspicion of a disease or condition that contraindicates the use of an investigational drug or that may affect the interpretation of the results or render the patient at high risk for treatment complications
- Illnesses or conditions that interfere with their capacity to understand, follow, and/or comply with study procedures
- Treatment with investigational therapy with therapeutic intent within 28 days prior to enrollment
- Administration of a live, attenuated vaccine within 4 weeks before enrollment or anticipation that such a live attenuated vaccine will be required during the study

Patients must not receive live, attenuated influenza vaccines (e.g. FluMist[®]) within 4 weeks prior to enrollment, during treatment, and for 5 months following the last dose of atezolizumab or chemotherapy.

- Prior treatment with CD137 agonists or immune checkpoint blockade therapies, anti-PD-1, and anti-PD-L1 therapeutic antibodies
- Treatment with systemic immunosuppressive medications (including, but not limited to corticosteroids, cyclophosphamide, azathioprine, methotrexate, thalidomide, and anti-tumor necrosis factor [anti-TNF] agents) within 1 week prior to enrollment

Patients who have received acute systemic immunosuppressant medications (e.g., use of corticosteroids for nausea, vomiting, or management of or premedication for allergic reactions) may be enrolled in the study after discussion with and approval by the Medical Monitor. In those patients, the need and length of the washout period prior to enrollment will also be established in conjunction with the Medical Monitor.

The use of inhaled corticosteroids for chronic obstructive pulmonary disease, mineralocorticoids (e.g., fludrocortisone) for patients with orthostatic hypotension, and low-dose supplemental corticosteroids for adrenocortical insufficiency are allowed.

- History of severe allergic, anaphylactic, or other hypersensitivity reactions to chimeric or humanized antibodies or fusion proteins
- Known hypersensitivity to biopharmaceuticals produced in Chinese hamster ovary cells or any component of the atezolizumab formulation
- History of allergic reactions to carboplatin or etoposide or to any of its excipients (etoposide)
- Known hypersensitivity to venetoclax or to any of its excipients

- Administration of the following agents within 7 days prior to the first dose of study drug:
 - Steroid therapy for anti-neoplastic intent (stable steroid mediation not more than 10 mg prednisolone per day or an equivalent dose of other corticosteroids for controlling CNS metastases is acceptable)
 - Strong or moderate CYP3A inhibitors (see Appendix 6 for examples)
 - Strong or moderate CYP3A inducers (see Appendix 6 for examples)

Additional restrictions for on-study use of CYP3A inhibitors/inducers are outlined in Section 4.4.2.

- Consumption of grapefruit, grapefruit products, Seville oranges (including marmalade-containing Seville oranges), or starfruit (carambola) within 3 days before within 3 days prior to the first dose of study drug
- Malabsorption syndrome or other condition that would interfere with enteral absorption
- Illicit drug or alcohol abuse within 12 months prior to screening, in the investigator's judgment
- Inability or unwillingness to swallow a large number of tablets
- History of inflammatory bowel disease (e.g., Crohn's disease or ulcerative colitis) or active bowel inflammation (e.g., diverticulitis)

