1.4 BACKGROUND ON ATEZOLIZUMAB

Atezolizumab is a humanized IgG1 monoclonal antibody that targets PD-L1 and inhibits the interaction between PD-L1 and its receptors, PD-1 and B7-1 (also known as CD80), both of which function as inhibitory receptors expressed on T cells. Therapeutic blockade of PD-L1 binding by atezolizumab has been shown to enhance the magnitude and quality of tumor-specific T-cell responses, resulting in improved anti-tumor activity (Fehrenbacher et al. 2016; Rosenberg et al. 2016). Atezolizumab has minimal binding to Fc receptors, thus eliminating detectable Fc-effector function and associated antibody-mediated clearance of activated effector T cells.

Atezolizumab shows anti-tumor activity in both nonclinical models and cancer patients and is being investigated as a potential therapy in a wide variety of malignancies. Atezolizumab is being studied as a single agent in the advanced cancer and adjuvant therapy settings, as well as in combination with chemotherapy, targeted therapy, and cancer immunotherapy.

Safety findings of single-agent atezolizumab across multiple tumor types are consistent with the known mechanism of action of atezolizumab and the underlying disease. Overall, treatment with atezolizumab is well tolerated with a manageable adverse event profile. Currently, the most commonly reported adverse events (≥10%) include fatigue, decreased appetite, cough, nausea, dyspnea, constipation, diarrhea, pyrexia, vomiting, arthralgia, back pain, asthenia, anemia, pruritus, rash, headache, and peripheral edema.

The adverse events observed with atezolizumab in combination with chemotherapy and/or targeted therapies are consistent with the known risks of the individual study treatment. Systemic immune activation, characterized by an excessive immune

Venetoclax—F. Hoffmann-La Roche Ltd Page 40 of 214 Protocol GO41864, Version 2 response, is a potential risk associated with atezolizumab when used in combination with another immunomodulating compound. There are no atezolizumab-related adverse events that are exacerbated when used in combination with other agents.

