Once the *RP2D* in the induction and in the maintenance *phase* has been established from the dose-escalation cohorts, additional patients will be enrolled in the dose-expansion cohort to further assess the safety and efficacy of venetoclax in combination with carboplatin, etoposide and/or atezolizumab. If the RP2D for venetoclax during induction was established, then the dose-expansion cohort will continue to test venetoclax in both induction and maintenance. If significant toxicity and DLTs in induction preclude identification of an RP2D for venetoclax in induction treatment, then the safety and efficacy of venetoclax will only be investigated in dose-expansion in the maintenance setting. If the maintenance-only cohort is expanded, then prior treatment with 4 induction cycles of carboplatin and etoposide as well as at least 3 cycles of *atezolizumab* will be required. If there are concerns about the tolerability of venetoclax during the dose-expansion stage, then a lower dose or alternative dosing schedule may be explored based on the severity and timing of DLTs as well as the specific adverse events encountered. For example, consideration may be given to enrolling an expansion cohort at the next lower dose level (as defined in dose-escalation stage; see Section 3.1.2). Decision making will integrate cumulative safety and efficacy data during treatment and will be led by the Medical Monitor in consultation with the Principal Investigators and a committee composed of at a minimum the following Sponsor representatives: statistician, safety scientist, PK scientist, and clinical scientist.

DOR=duration of response; ECOG=Eastern Cooperative Oncology Group; ES=extensive-stage; INV=investigator; MTD=maximum tolerated dose; ORR=objective response rate; PFS=progression-free survival; Q3W=every 3 weeks; RECIST v1.1=Response Evaluation Criteria in Solid Tumors, Version 1.1; RP2D-I=recommended Phase II dose for induction; RP2D-M=recommended Phase II dose for maintenance; SCLC=small cell lung cancer.

3.1.6 Treatment after Disease Progression

During the study, patients who meet criteria for disease progression per RECIST v1.1 and show evidence of clinical benefit may continue treatment at the investigator's discretion, provided that the patients meet all of the following criteria:

- Evidence of clinical benefit, as assessed by the investigator

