4.1.1 Inclusion Criteria

Dose Escalation, Maintenance Arm A

- Patients with ES-SCLC who have completed 4-6 cycles of carboplatin and etoposide induction chemotherapy, with or without *atezolizumab*, as their first-line therapy for extensive-stage disease and have responded (CR or PR) or have SD are eligible for the maintenance arm of the study.
- All side effects attributed to prior anti-cancer therapy must have resolved to Grade 1 or baseline.
- A maximum of 8 weeks (56 days) is allowed between last chemotherapy dose (Cycle 4, Day 3) given in induction and the start of maintenance therapy.

Dose Escalation, Induction Arm B

- Patients with no prior systemic treatment for ES-SCLC are eligible for this study.
- ANC \geq 1,500 cells/µL without granulocyte colony-stimulating factor support

Dose Expansion, Maintenance-Only

• Patients with ES-SCLC who have completed 4 cycles of carboplatin and etoposide induction chemotherapy and at least 3 cycles of *atezolizumab* as their first-line therapy for extensive-stage disease and have *responded* (*CR or PR*) or have SD are eligible for the maintenance arm of the study.

Dose Escalation (Arms A and B) and Dose Expansion

- Signed Informed Consent Form
- Age \geq 18 years at time of signing Informed Consent Form
- Ability to comply with the study protocol, in the investigator's judgment
- ECOG performance status of 0 or 1
- Patients must be able to swallow pills
- Histologically or cytologically confirmed diagnosis of ES-SCLC per the Veterans Administration Lung Study Group (VALG) staging system
- Patients who received prior chemoradiotherapy for limited-stage SCLC must have been treated with curative intent and experienced a treatment-free interval of at least 6 months since last chemotherapy, radiotherapy, or chemoradiotherapy cycle prior to diagnosis of ES-SCLC
- Patients with a history of treated CNS metastases that are currently asymptomatic are eligible, provided they meet all of the following criteria:
 - Only supratentorial and cerebellar metastases allowed (i.e., no metastases to midbrain, pons, medulla or spinal cord)
 - No ongoing requirement for corticosteroids as therapy for CNS disease
 - No evidence of interim progression between the completion of CNS-directed therapy and enrollment
 - Patients with new asymptomatic CNS metastases detected at the screening scan must receive radiation therapy and/or surgery for CNS metastases.

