9.2 PROTOCOL DEVIATIONS

The investigator should document and explain any protocol deviations. The investigator should promptly report any deviations that might have an impact on patient safety and data integrity to the Sponsor and to the IRB/EC in accordance with established IRB/EC policies and procedures. The Sponsor will review all protocol deviations and assess whether any represent a serious breach of Good Clinical Practice guidelines and require reporting to health authorities. As per the Sponsor's standard operating procedures, prospective requests to deviate from the protocol, including requests to waive protocol eligibility criteria, are not allowed.

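### As written, the ban on prior anti-PD-L1 antibodies leaves the maintenance-only expansion with no eligible patients and bars atezolizumab-pretreated patients from Arm A

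*Combined protocol and SAP*

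**What the plan says.** The exclusion list in Section 4.1.2, repeated in the synopsis, contains this item: "Prior treatment with CD137 agonists or immune checkpoint blockade therapies, anti-PD-1, and anti-PD-L1 therapeutic antibodies". Unlike the inclusion list, the exclusion list has no cohort headings.

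For the maintenance-only expansion, Section 4.1.1 describes eligible patients as having "completed 4 cycles of carboplatin and etoposide induction chemotherapy and at least 3 cycles of" atezolizumab as first-line therapy. Section 3.1.5 repeats this as a condition: "prior treatment with 4 induction cycles of carboplatin and etoposide as well as at least 3 cycles of *atezolizumab* will be required". For Arm A of the dose escalation, Section 4.1.1 admits patients "who have completed 4-6 cycles of carboplatin and etoposide induction chemotherapy, with or without" atezolizumab.

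On the drug's class, Section 1.4 says: "Atezolizumab is a humanized IgG1 monoclonal antibody that targets PD-L1". Section 4.5.1 requires all eligibility criteria to be confirmed before enrollment. Section 9.2 says that prospective deviations, including "requests to waive protocol eligibility criteria, are not allowed".

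**The concern.** The two lists pull in opposite directions on the same drug. What the maintenance-only expansion requires, and Arm A permits, the exclusion list forbids for everyone.

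The main stake is the fallback route. Under Section 3.1.5, if toxicity in induction prevents an RP2D from being identified there, venetoclax is expanded in the maintenance setting only. That cohort would then be the sole source of the primary efficacy endpoint, ORR. Section 6.1 treats it as a planned path, with its own precision statement at an observed ORR of 5%.

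Arm A is affected from the start. It runs first, it sets the maintenance RP2D, and Arm B opens only after it. Section 3.3.1 calls atezolizumab plus carboplatin and etoposide the current first-line standard in the United States and European Union. Read literally, the exclusion turns away everyone who received that regimen.

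**Working it through.** The point rests on no sample-size or power figure. The check is to set the rules side by side and look for any text that reconciles them.

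| Cohort | Prior atezolizumab under inclusion (4.1.1, 3.1.5) | Prior anti-PD-L1 antibody under exclusion (4.1.2, synopsis) | Who can enter |
|---|---|---|---|
| Maintenance-only expansion | Required, at least 3 cycles | Forbidden | Nobody |
| Arm A | Allowed, not required | Forbidden | Only patients whose induction did not include atezolizumab |
| Arm B | No prior systemic treatment for ES-SCLC | Forbidden | No conflict |
| Induction-plus-maintenance expansion | Not required | Forbidden | No conflict |

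**Maintenance-only expansion.** Let I be the patients with at least 3 prior cycles of atezolizumab and E the patients with any prior anti-PD-L1 antibody. Atezolizumab is such an antibody (Section 1.4), so every member of I is in E. The eligible set, I without E, is empty. Section 4.1 plans an estimated 20 expansion patients in total. If the expansion is maintenance-only, 0 of those 20 can satisfy both lists.

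**Arm A.** Section 6.1 plans two cohorts of 3 to 6 patients: 2 × 3 = 6 to 2 × 6 = 12 places. These can still be filled, but not by anyone who received atezolizumab in induction. The documents do not say what share of candidates that is, so the loss cannot be sized.

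**Possible ways out:**

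- *Cohort restriction.* None: the exclusion list applies to all cohorts.
- *Time window or exception.* None on this item. Other items do state them where intended: investigational therapy has a 28-day window, systemic immunosuppressants a 1-week window, and autoimmune disease and hepatitis B and C have listed exceptions.
- *First exclusion item.* It bars agents outside the protocol and other partners to carboplatin and etoposide during induction. That suggests atezolizumab in induction was meant to be acceptable, but it does not qualify the separate anti-PD-L1 item.
- *Medical Monitor discretion.* The case-by-case allowance in Section 4.4.2 concerns concomitant medication on study, not this entry criterion.
- *Waiver.* Closed by Section 9.2.

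No text resolves the conflict.

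**The case against.** The strongest reply is that the intent is plain. Prior atezolizumab is named as allowed or required, by cohort, in Sections 3.1.1, 3.1.5 and 4.1.1 and in the synopsis, and the first exclusion item points the same way. On this view the anti-PD-L1 item was simply not updated, so this is a drafting slip and not a design decision. That is probably right about the cause. It does not help a site, which must confirm every criterion and may not ask for a waiver.

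The reply also limits the size of the problem. The maintenance-only expansion is conditional: the 20 places go to induction plus maintenance if an induction RP2D is found, and that expansion is unaffected. Arm A is narrowed, not closed. Both limits stand.

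One further worry is that the maintenance RP2D would come only from patients without prior atezolizumab and then be applied to patients who have had it. This is secondary. Arm A already differs by design from the Arm B patients who reach maintenance after four cycles of venetoclax-containing induction. The exclusion could widen that difference but does not create it.

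Nor is it certain how sites would behave. They might screen-fail patients, enroll in breach of the exclusion, or query the sponsor.

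**Conclusion.** The concern holds. As written, the maintenance-only expansion has no eligible population: 0 of 20 if it is opened. Arm A's 6 to 12 places are closed to patients who received atezolizumab in induction.

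This assumes only that atezolizumab counts as an anti-PD-L1 antibody, as Section 1.4 states, and that both lists are applied as written. The contradiction stands in the current text of both the synopsis and the body. It must be fixed, because a planned route to the primary efficacy endpoint cannot enroll without breaching the protocol. For Arm A the demonstrated effect is narrowing, of unknown extent.

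**What to change.** Reconcile the anti-PD-L1 exclusion in Section 4.1.2 and the synopsis with Sections 4.1.1 and 3.1.5 and their synopsis counterparts. If the inclusion criteria state the sponsor's intent, add an exception to the exclusion: atezolizumab given with carboplatin and etoposide as first-line induction for ES-SCLC is permitted for Arm A and required for the maintenance-only expansion. Leave the exclusion unchanged for the induction cohorts. This carries the sponsor's own inclusion rule into the exclusion list and adds no new one.

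The same amendment should correct general statements that do not fit the maintenance-only cohorts: Section 1.6.2 describes the study population as having had no prior systemic treatment, and Sections 2 and 3.3.1 describe it as chemotherapy-naive for extensive-stage disease.

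The cost is one clause in each of two places plus those wording corrections, with no extra patients or procedures. Under Section 9.7 the change needs ethics approval and, where locally required, regulatory approval before use.
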